### **5.5.6 General Procedures for Handling Missing Data**

Every reasonable effort will be made to continue follow-up of all study participants, including those who discontinue randomized therapy, to prevent data loss. It is recognized that missing values represent a potential source of bias in a clinical trial and so every effort will be undertaken to fulfill all the requirements of the protocol concerning the collection and management of data.

For the primary time to event analysis, the only possible patient outcome is an observed FAP-related event or a censored observation. Participants who are lost to follow-up will be censored at the time their status is last known, based upon data collected at the last recorded clinic visit. For patients who may have missed a study visit, every effort will be made to obtain endoscopic results at their close-out visit and those endoscopy results will be used for the primary analysis.

Secondary analysis data include the presence of a specific genetic mutation, and urinary metabolite concentrations (see Section 3.2.3). The main analysis of the secondary objectives will include collected data only, without imputing or weighting data to compensate for missing data. For sensitivity analyses involving secondary endpoints with missing data, we will use the last observation carried forward (LOCF) method to complete the missing data. Any sensitivity analysis that incorporates LOCF will be clearly noted. Sensitivity analyses of these data will be performed to explore study results more fully, in a manner consistent with ICH Guidance “*E9 Statistical Principles for Clinical Trials (February, 1998)*”.

All available efficacy and safety data will be included in data listings and tabulations. Data that are potentially spurious or erroneous or appear as outliers will be examined using standard data management operating procedures, prior to database lock and statistical analysis. These procedures will be fully described in the study report.

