#### **12.7. General Procedures for Handling of Missing Data**

Every reasonable effort will be made to continue follow-up of all study participants, including those who discontinue randomized therapy, to prevent data loss. It is recognized that missing values represent a potential source of bias in a clinical trial and so every effort will be undertaken to fulfill all the requirements of the protocol concerning the collection and management of data.

For the primary time to event analysis, the only possible patient outcome is an observed FAP-related event, or a censored observation. Participants who are lost to follow-up for reasons deemed unrelated to their health status will be censored at the time their status is last known, based upon data collected at the last recorded clinic visit. For patients who may have missed a study visit, every effort will be made to obtain endoscopic results at their close-out visit and those endoscopy results will be used for the primary analysis.

Secondary analysis data include the presence of a specific genetic mutation, and urinary metabolite concentrations (See Section 12.2). The main analysis of the secondary objectives will include collected data only, without imputing or weighting data to compensate for missing data. For sensitivity analyses involving secondary endpoints with missing data, we will use the last observation carried forward (LOCF) method to complete the missing data. Any sensitivity analysis that incorporates LOCF will be clearly noted. Sensitivity analyses of these data will be performed to explore study results more fully, in a manner consistent with ICH Guidance “*E9 Statistical Principles for Clinical Trials* (February, 1998)”.

All available efficacy and safety data will be included in data listings and tabulations. Data that are potentially spurious or erroneous or appear as outliers will be examined using standard data management operating procedures, prior to database lock and statistical analysis.

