### 3.2.3 Secondary Efficacy Analyses

Any improvement observed by the investigator during upper gastrointestinal (UGI) and lower gastrointestinal (LGI) visualization (i.e. endoscopy and colonoscopy) at the 6 and 12-month study visits will be described using the variables UGI Observed Improvement (UGIOI), and LGI Observed Improvement (LGIOI). Each patient will have one pair of UGIOI and LGIOI outcomes.

UGIOI and LGIOI are binary outcomes derived from numerical determinations (henceforth, “investigator change scores” or more briefly, “scores”) assigned by the investigator during each procedure, using a scale (-2, -1, 0, +1, +2) which corresponds, respectively, to the investigator’s overall qualitative assessment of: much worse, worse, no change, improved, much improved. At the month 6 procedures the investigator scores UGI and LGI findings as changes from baseline. At the month 12 procedures, the UGI and LGI findings are scored relative to the month 6 procedures.

The UGIOI (and respectively, the LGIOI) secondary endpoint independently summarizes the corresponding 6- and 12-month investigator change scores according to whether or not there was *any positive improvement* at either month 6 (compared to baseline) or at month 12 (compared to baseline or month 6), under the condition that there be *no worsening at either timepoint* (compared to the preceding timepoint). Here are the specific possibilities (where “Improvement” stands for either the UGIOI or LGIOI secondary endpoint):

- If the 6-month score is -2 or -1, Improvement=NO irrespective of the 12-month score.
- If the 6-month score is 0, then Improvement=YES if and only if the 12-month score is +1 or +2. Otherwise Improvement=NO.
- If the 6-month score is +1 or +2, then Improvement=YES if and only if the 12-month score is greater than or equal to 0. Otherwise Improvement=NO.

Any patient who drops out of the study before the month 12 assessment will be considered Improvement=NO.

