Patient preferences (or utilities) will also be assessed using the EuroQoL EQ-5D. Preference weights among the treatment arms will be determined using the EuroQoL EQ-5D assessment of individual health states[11, 12]. Quality-adjusted survival among the three treatment arms will be generated by multiplying the utility value by the amount of time spent in a specified health state.

The modified version of the Cancer Worry Scale will also be administered and it will be scored according to the guidance provided by Lerman *et al*[13].

HRQoL data will be obtained while patients are receiving treatment. At the time of an FAP-related event (primary outcome), additional long-term clinical follow-up and QoL data will not be obtained as part of this trial. Hence, HRQoL trends comparing the nine subsets will be obtained, but comparative longitudinal analyses defining the impact of an FAP-related event on QoL will not be feasible until subsequent long-term studies are performed.

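### LOCF, the only named method for missing secondary data, carries last values past FAP events in by-visit quality-of-life and polyamine summaries

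*SAP*

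**What the plan says.** SAP 5.5.6 sets the main secondary analysis as observed data only: "The main analysis of the secondary objectives will include collected data only, without imputing or weighting data to compensate for missing data". For sensitivity it says: "For sensitivity analyses involving secondary endpoints with missing data, we will use the last observation carried forward (LOCF) method to complete the missing data". Protocol 12.7 repeats this: "we will use the last observation carried forward (LOCF) method to complete the missing data". Both require any LOCF analysis to be flagged. The sentence that follows, "Sensitivity analyses of these data will be performed to explore study results more fully", points to ICH E9 but names no other method. The subsets in SAP 4.4 are populations, not ways of handling missing values.

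On why values go missing:
- Protocol 8.2.14 stops treatment at the first FAP event, and Protocol 4.2 describes such subjects as coming off study.
- SAP 5.6 collects quality of life only on treatment; after an event, "additional long-term clinical follow-up and QoL data will not be obtained as part of this trial".
- Protocol 8.2.14 still requires an event subject to complete the End of Treatment (EOT) assessments. Under Protocol 8.2.6 and 8.2.10 these include the quality-of-life questionnaires and polyamine urine.

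On how the data are used:
- SAP 5.5.4 compares continuous outcomes by ANCOVA at end of treatment.
- SAP 3.2.4 relates urinary polyamines at each study visit to arm and outcome, and SAP 5.6 promises quality-of-life trends.
- SAP 3.2.3 defines the binary upper and lower GI improvement endpoints (UGIOI, LGIOI) and gives drop-outs their own rule: "Any patient who drops out of the study before the month 12 assessment will be considered Improvement=NO".

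**The concern.** A missing-data sensitivity analysis should show whether a secondary result survives other plausible assumptions about the values not seen. LOCF makes one assumption, that nothing changes after the last visit. Here the usual reason for having no later visit is the very event the treatment is meant to delay, followed by stopping the drug. For polyamines, LOCF places an on-drug or just-off-drug level into off-drug time. For quality of life, it places a value from at or before the event into the period after it. Protocol 8.2.8 expects that for some subjects the indicated procedure will still be outstanding 30 days after the EOT visit, so even an EOT score can precede surgery. Filled values enter as if measured, so standard errors are too small. If the drug works, the single-agent arms have more filled values than the combination arm, and the distortion differs by arm. By-visit trends could then look more stable, or the arms more alike, than the data warrant.

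**Working it through.** **1. Reproduce the design figures (SAP 5.2, 5.3, Table 3.2).** Event-free at 24 months: 0.30 single agent, 0.60 (possibly 0.70) combination.
- HR = ln 0.60 / ln 0.30 = 0.4243.
- Schoenfeld events, two-sided 0.05, 85% power, 1:1: 4(1.960 + 1.036)² / (ln 0.4243)² = 48.86, so 49 as stated. With 0.70 on combination, HR = 0.296 gives 24.27, so 25 as stated.
- Expected events per 50 subjects: 50 × 0.70 = 35, against 50 × 0.40 = 20 or 50 × 0.30 = 15, as stated.

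**2. Share with an event by month m.** Using the SAP's exponential assumption, share = 1 − S^(m/24).

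| Month | Single agent (S = 0.30) | Combination (S = 0.60) | Ratio |
|---|---|---|---|
| 6 | 26.0% | 12.0% | 2.17 |
| 12 | 45.2% | 22.5% | 2.01 |
| 18 | 59.5% | 31.8% | 1.87 |
| 24 | 70.0% | 40.0% | 1.75 |

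With 0.70 on combination, the month-12 share is 16.3% (ratio 2.77) and the month-24 share 30% (ratio 2.33).

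If events are found at the six-monthly endoscopies, a subject with an event by month 12 has nothing from month 18 on. Empty slots through month 24, out of 50 × 4 = 200 per arm, are 50 × (0.260 + 0.452 + 0.595) ≈ 65 single agent and 50 × (0.120 + 0.225 + 0.318) ≈ 33 combination, a ratio of about 2.0.

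**3. Calibrate to blinded data (Protocol 3.2).** There were 53 events in 171 subjects as of June 2017, or 31.0%. Randomisation ran from July 2014 to April 2016 (Protocol 4.2), giving 14 to 35 months of follow-up. Assume uniform accrual, exponential times, equal single-agent hazards λ and no other loss. Solve [2F(λ) + F(λ × HR)]/3 = 53/171, where F is the event share averaged over follow-up.

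| Assumed HR | λ per month | Single agent, month 12 | Combination, month 12 | Ratio |
|---|---|---|---|---|
| 0.4243 | 0.0194 | 20.8% | 9.4% | 2.21 |
| 0.6 | 0.0178 | 19.3% | 12.1% | 1.60 |
| 0.8 | 0.0164 | 17.9% | 14.6% | 1.23 |
| 1.0 | 0.0153 | 16.8% | 16.8% | 1.00 |

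**4. End-of-treatment ANCOVA.** An event subject who completes the required EOT visit has a value at the analysed time point. Nothing is missing, and LOCF fills nothing for that subject.

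**5. UGIOI and LGIOI.** The month-12 score is a change, not a level: "At the month 12 procedures, the UGI and LGI findings are scored relative to the month 6 procedures". The scoring rule is "If the 6-month score is +1 or +2, then Improvement=YES if and only if the 12-month score is greater than or equal to 0". A carried +1 or +2 would therefore become improvement, while a carried 0 or negative score stays at no improvement. The result could change only for a subject with a positive month-6 score on that tract and no month-12 score, and only if LOCF overrode the drop-out rule. If a share q of subjects with an event by month 6 scored positive, the credit would be 0.260q against 0.120q. The documents do not give q. For q from 10% to 50%, that is 1.3 to 6.5 single-agent and 0.6 to 3.0 combination subjects per 50.

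**The case against.** The strongest defence is that no main comparison uses LOCF. The main secondary analysis does not impute, the gated tests of UGIOI and LGIOI in SAP 3.2.3 do not call on it, and any LOCF output must be labelled. SAP 5.6 also states that longitudinal analysis of an event's impact on quality of life will not be feasible, so no post-event claim rests on these values. All of this stands, and it limits the point to the value of the sensitivity analysis.

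Three stronger readings are tempting, and the documents do not support them.
- A reader might infer that LOCF will credit event subjects with endoscopic improvement. Taking q at 0.2 to 0.4, the credit would remove (0.260 − 0.120)q, or 2.8 to 5.6 points, of arm difference. But SAP 3.2.3 has a specific rule scoring drop-outs as not improved, event subjects come off study, and no passage lets the general rule override it. On the tract that caused the event, a positive score is also unlikely. Any credit would tend to favour the single-agent arms, so it would not inflate the sponsor's claim.
- A reader might infer that 59% of single-agent and 32% of combination values in the continuous comparison are carried forward. Those month-18 shares would apply to a fixed month-24 summary. The specified comparison is at end of treatment.
- A reader might take the 2:1 imbalance as established. It is a projection under the design alternative and disappears under the null.

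The defence leaves two gaps. The SAP never says in terms that an FAP event before month 12 counts as dropping out, and it does not reconcile that rule with observed data only. SAP 5.5.6 also promises continued follow-up after stopping therapy, while SAP 5.6 says none is obtained after an event.

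**Conclusion.** The point holds as a weakness in the named sensitivity analysis, not in any main test. LOCF is the only specified way of completing missing secondary data. In by-visit quality-of-life and polyamine summaries it would extend a value past an informative exit, with no allowance for uncertainty. The subjects affected after month 12 are about 45% single agent and 23% combination under the design assumptions. They are about 21% and 9% when calibrated to the blinded event count at the design hazard ratio, and about 17% in each arm under the null. These shares rest on exponential times and, for the calibration, on assumed uniform accrual with no other loss. They count values filled. The bias in scale points cannot be computed, because the documents give no post-event change, and missingness from causes other than FAP events is not quantified. For UGIOI and LGIOI the finding is only that the precedence of the drop-out rule should be written down. The change is worth making, because the sensitivity analysis as planned cannot test the assumption most in doubt.

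**What to change.** Delete the LOCF sentence in SAP 5.5.6 and Protocol 12.7 and replace it as follows.
- **Continuous and quality-of-life outcomes by visit:** a mixed model for repeated measures on all collected visits, with baseline, stratum, visit, arm and arm-by-visit. Label it as a hypothetical effect under missing at random, as if collection had continued; it is not a while-event-free effect. Add delta-adjusted or reference-based multiple imputation for values after an FAP event.
- **UGIOI and LGIOI:** add one sentence saying that an FAP event before the month-12 score counts as Improvement=NO and that SAP 3.2.3 takes precedence over SAP 5.5.6. For scores missing for other reasons, use multiple imputation within arm and stratum, with a tipping-point table, as sensitivity analysis.
- **Follow-up:** reconcile the promise in SAP 5.5.6 with the statement in SAP 5.6.

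The cost is wording in two documents and modest programming, with no new data collection. The drawback is reliance on missing at random in the mixed model, which the delta and tipping-point analyses are there to test.

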### **5.5.7 Subgroup Analyses**

Subgroups will be analyzed in the spirit of exploratory analyses including but not limited to the various study populations (see Section 4) and separately within each disease-prognosis stratum.

## **5.6 Health Related Quality of Life (HRQoL) Statistical Methods**

For this study four (4) instruments to measure HRQoL and patient preferences or utilities will be administered to subjects at baseline and at 3, 6, 12, 18, 24, 30, 36, 42 and 48 months post-enrollment/end of treatment. These instruments include the EORTC QLQ-C30, EORTC QLQ-CR29, EQ-5D, and a modified Cancer Worry Scale.

- The EORTC QLQ-C30 is a self-administered quality of life questionnaire[9] with multi-dimensional scales. It consists of both multi-item scales and single item measures, including five functioning domains, a global quality of life domain, three symptom domains and six single items.
- The EORTC QLQ-CR29 gastrointestinal/colorectal sub-module[10] is composed of 4 functional and 18 symptom related sub-scales. The 4 functional scales include body image, weight, anxiety and sexual function. The symptom related scales include single item and multi-item questions concerning stool frequency, bleeding and mucous discharge, stool leakage, abdominal bloating, flatulence, embarrassment and site-specific pain among others.
- The EuroQol EQ-5D is a standardized instrument for use as a measure of health outcome and is applicable to a wide range of health conditions and treatments[11, 12]. It provides a simple descriptive profile and a single index value for health status.

- The Cancer Worry Scale[13] is a brief psychometric instrument that was designed to assess both the frequency of worrying about “getting cancer some day” and measuring the impact of worry on mood and performing daily activities. This scale was originally developed by Caryn Lerman and her colleagues to study breast cancer and has been modified for use in this FAP trial.

The validity and reliability of both the QLQ-C30 and the QLQ-CR29 questionnaires have been studied by the EORTC Study Group on Quality of Life and both instruments will be scored according to the EORTC Scoring Manual and analyzed accordingly. For each single item or multi-item sub-scale, a linear transformation will be applied to standardize raw scores to range between 0 and 100. HRQoL secondary endpoints will include all single item or multi-item sub-scales from both the EORTC QLQ-C30 and QLQ-CR29 and patients will be considered as deteriorated (or improved) for a given single item or multi-item sub-scale if their change score from baseline was 10 points or more on the standardized scale.

Patient preferences (or utilities) will also be assessed using the EuroQoL EQ-5D. Preference weights among the treatment arms will be determined using the EuroQoL EQ-5D assessment of individual health states[11, 12]. Quality-adjusted survival among the three treatment arms will be generated by multiplying the utility value by the amount of time spent in a specified health state.

The modified version of the Cancer Worry Scale will also be administered and it will be scored according to the guidance provided by Lerman *et al*[13].

HRQoL data will be obtained while patients are receiving treatment. At the time of an FAP-related event (primary outcome), additional long-term clinical follow-up and QoL data will not be obtained as part of this trial. Hence, HRQoL trends comparing the nine subsets will be obtained, but comparative longitudinal analyses defining the impact of an FAP-related event on QoL will not be feasible until subsequent long-term studies are performed.

## 5.7 Dietary Assessment

The Food Frequency Questionnaire (FFQ) is the most common dietary assessment tool used in large epidemiologic studies of diet and health. The self-administered FFQ booklet asks participants to report the frequency of consumption and portion size of approximately 125 line items over a defined period of time (e.g. the last month; the last three months). Each line item is defined by a series of foods or beverages. Additional questions on food purchasing and preparation methods enable the analysis software to further refine nutrient calculations. The FFQ was developed by the Nutrition Assessment Shared Resource (NASR) of the Fred Hutchinson Cancer Research Center. NASR periodically updates its standard FFQ to reflect U.S. food consumption patterns and major changes in the market place[14, 15]. Data from the FFQ will be analyzed using a polyamine database[16-18] and will calculate the average daily levels of putrescine, spermidine, and spermine in the diet. Dietary assessments via the FFQ will be obtained at baseline, months 12, 24, 36, 42 (only if end of treatment), and 48/end of treatment for subjects at North American (U.S. and Canada) sites only. Clinical study sites outside of North America will not be included because the foods on the North American food frequency questionnaire are not the same as those widely consumed in Europe and elsewhere.

## 6. RANDOMIZATION ALGORITHM AND STRATIFICATION FACTORS

At least 150 eligible patients will be randomized in this study. Patients will be randomized to one of three treatment groups in equal proportions (i.e., 1:1:1 randomization): 1) CPP-1X plus sulindac, 2) CPP-1X-placebo plus sulindac, 3) CPP-1X plus sulindac placebo.

A stratified randomization procedure will be used with stratification based on FAP-related time-to-first-event prognosis. The event prognosis groups are represented by 1) best (i.e., longest projected time to first FAP-related event) - rectal/pouch polyposis, 2) intermediate - duodenal polyposis, and 3) worst - pre-colectomy. If a subject has two or more of these disease sites, the most severe prognosis stratum will be assigned for randomization (e.g. worst > intermediate > best). Since an individual may have more than one disease site involved, the trial will assess time to any defined FAP-related event in the patient as a whole. In order to minimize potential treatment arm imbalance a centralized randomization process will be used to balance among treatment groups within prognostic strata.

## 7. OTHER ISSUES AND FURTHER DETAILS

### 7.1 Statistical Software Used in Data Analysis

All analyses will be performed using SAS statistical analysis software version 9.1 or later. If other software is used (i.e. WinNonPop for population pharmacokinetics, SAS macros for futility analysis, etc.), it will be clearly described in the clinical and statistical study reports.

### 7.2 Draft Tables, Listings and Figures

The TLF (Tables, Listings, Figures) templates and shells are noted as Ver. 2.0, October 6, 2014 (SAP Ver. 3.0 September 30, 2014) based on revision provided from Data Management/Statistical Group at Ockham now Chiltern. These draft templates have been removed as an Appendix to the amended SAP and are available upon request.

### 7.3 Details of Calculating the Stratified Log-rank Z-Score

Patient follow-up will be analyzed in continuous time, although it is recognized that FAP event detection will cluster around scheduled study visits, at months 6, 12, 18, 24, 30, 36, 42 and 48 and event times may be tied as follow-up time is measured only to the nearest day. Censorings are possible at the baseline visit (month 0) for patients who dropped out of the trial before their first follow-up visit. The primary test statistic will be the stratified log-rank statistic. Each two-arm comparison will be performed separately. This will be implemented in SAS by specifying the TIES=DISCRETE option in PROC PHREG. The single agent treatments, respectively, will be coded as 1 and the combination treatment will be coded as 0. The square root of the score test chi-squared statistic will be calculated and the *sign* of the estimated log hazard ratio (+ if the HR>1 and – if the HR<1) will be attached. This results in the stratified log-rank Z-score. In symbols,  $Z_k = \text{sign}(\hat{\beta}) \times \sqrt{X^2}$ , where  $\hat{\beta}$  denotes the estimated log hazard ratio coefficient for treatment *A* in the Cox model and where  $X^2$  denotes the SCORE TEST chi-squared statistic reported within the “Testing Global Null Hypothesis: BETA=0” table at the top of the PHREG results section.

The following sample PHREG procedure could be used in SAS to derive the stratified log-rank Z-score:

```
proc phreg data=TwoArmData;
  model time*censor(1) = Treatment / rl ties=discrete;
```

```

strata Stratification_Factor;
title "Stratified Cox Regression Analysis for Single Agent vs Combination";
run;
quit;

```

NB: The model includes the variables time, censor, and treatment, only.

